4.5.2 Secondary Efficacy Endpoints

The secondary efficacy endpoints are listed in Section 2.1.2. At the time of primary analysis, all secondary endpoints will be evaluated based on data from baseline to Week 48 (see Section 2.4). At the time of the final study analysis, all secondary endpoints will be evaluated based on data from baseline to Week 96.

Analysis of secondary efficacy endpoints assessed by mesopic microperimetry will be based on the microperimetry-analysis population. Statistical inferences for efficacy endpoints based on microperimetry assessments will be based on pooled data from Studies GX29176 and GX29185. Analysis of all other secondary efficacy endpoints will be based on the ITT patient population.

Hypothesis testing for three key secondary endpoints will be performed in the order specified in Section 4.5.2.1 based on the Week 96 timepoint. Subgroup analyses (Section 4.5.2.2) for the key secondary efficacy endpoints will be performed.

Treatment-effect related analyses to compare each lampalizumab treatment arm (Q4W or Q6W) and the pooled sham arm for secondary efficacy endpoints will be undertaken as follows. In general, continuous secondary endpoints will be analyzed using a MMRM analysis, with change from baseline as the response variable. For the Week 48 analyses, post-baseline visits, up to and including Week 48, will be included. For the Week 96 analyses, post-baseline visits, up to and including Week 96, will be included. Independent variables for treatment arm, study visit (categorical variable), treatment arm by study visit interaction, baseline value of the endpoint, and the randomization stratification factors and baseline covariates as described in Section 4.5 will be included in the model. An unstructured covariance matrix will be used to model the within-subject errors. If there are convergence problems with the model, then a heterogeneous compound symmetry covariance structure will be used.

In general, binary secondary endpoints will be analyzed using a logistic regression model. The model will include independent variables for treatment arm, baseline value of the endpoint (continuous scale), and the randomization stratification factors and baseline covariates as described in Section 4.5, as appropriate. If the response rate is low, an unadjusted analysis may be performed. Analyses will be based on the observed data for the timepoint, with no imputation for missing data.

For analyses of BCVA, the model will include the major assessment timepoints of Weeks 12, 24, 36, 48, 60, 72, 84, and 96 that are in common between the Q4W and Q6W dosing arms. In addition, the stratification factor of baseline BCVA category will not be included in the model, given baseline BCVA is included as a continuous covariate.

Reading speed will be calculated per the MNRead or Radner user's manuals, with no adjustment for reading inaccuracy. An addition step to cap resulting reading speed values at a maximum of 300 words per minute will be implemented. Values above 300 words per minute exceed values reported in the literature for adults with no vision impairment for MNRead (Calabrese et al. 2016) or Radner (Radner et al. 2002; Radner and Diendorfer 2014) assessments. Maximum reading speed will be calculated as the mean of the three highest reading speeds obtained per the user's manuals. Data collected via the two reading charts will be pooled for analysis and the model will include an additional covariate for reading chart type (MNRead or Radner). Additional subgroup analyses will be performed to assess the consistency of finding across the two reading charts (see Section 4.5.2.2).

NEI VFQ-25 scores (composite, near activity subscale, and distance activity subscale) and mean FRI Index scores will be calculated per the scoring algorithms in the corresponding user's manuals.

For analyses of binocular maximum reading speed, NEI VFQ-25 composite score, NEI VFQ-25 near activity subscale score, NEI VFQ-25 distance activity subscale score, and mean FRI Index score, an additional adjustment for baseline BCVA of the better seeing eye will be included (instead of study eye baseline BCVA [20/50 or better vs. worse than 20/50]). In the event that baseline BCVA is missing for the study or fellow eye (but not both), then the non-missing baseline BCVA will be used for this covariate.

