Table 7 Power and Minimum Detectable Difference for Primary Endpoint in This Study

Endpoint	Target Treatment Effect	Two-Sided $\alpha=0.0495$	
		Power	MDD
Mean change from baseline in GA area at 1 year in biomarker-positive patients (n=188 per arm)	$\Delta=1.45$ mm ² (approximately 40% ^a reduction) SD=2.51	>95%	0.56 mm ² (approximately 15% ^a reduction)
Mean change from baseline in GA area at 1 year in biomarker-negative patients (n=124 per arm)	$\Delta=0.66$ mm ² (approximately 40% ^a reduction) SD=1.68	80%	0.46 mm ² (approximately 28% ^a reduction)

GA=geographic atrophy; MDD=minimum detectable difference.

The sample size takes into account the dropout rate of 15% by 1 year. The power and MDD are for each comparison between one lampalizumab treatment group and the pooled sham group.

^a Relative to the sham group and assuming the mean change from baseline in GA area at 1 year (48 weeks) is 1.645 mm² for biomarker-negative group and 3.631 mm² for biomarker-positive group.

The Sponsor may conduct a masked evaluation of the variance of the primary efficacy endpoint and study dropout rate before the end of enrollment and compare the information to the assumptions used in planning the study. If this comparison suggests the initial assumptions for the dropout rate and/or the variance of the primary efficacy endpoint were substantially lower, and the study is consequently underpowered, the study sample size will be increased to maintain the desired study power and safety database. Details will be provided in the SAP.

For patients who are eligible to undergo a microperimetry assessment, at least 46 CFI profile biomarker-positive patients per lampalizumab treatment group and 23 CFI profile biomarker-positive patients per sham group will provide 80% power to detect a targeted difference of 6.91 points with a standard deviation of 9.88 points between each

lampalizumab treatment group and the pooled sham group in the change from baseline in the number of scotomatous points at 2 years. Calculation was based on a two-sided t-test at $\alpha=0.05$ level with the assumption of a 25% dropout rate by 2 years.

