2.1.2 Secondary Efficacy Endpoints

The following secondary efficacy endpoints will be assessed over time up to Week 96, with formal statistical testing at Week 96. Hypothesis testing for three key secondary endpoints will be performed in the order specified in Section 4.5.2.1 based on the Week 96 timepoint.

- Change from baseline in number of absolute scotomatous points as assessed by mesopic microperimetry
 - Assessed for subset of patients at selected study sites only. Endpoint will be evaluated based on pooled data from GX29176 and GX29185.

- Change from baseline in mean macular sensitivity as assessed by mesopic microperimetry
 - Assessed for subset of patients at selected study sites only. Endpoint will be evaluated based on pooled data from GX29176 and GX29185.
- Change from baseline in best corrected visual acuity (BCVA) as assessed by the Early Treatment Diabetic Retinopathy Study (ETDRS) chart at a starting distance of 4 m
- Patients with < 15 letters loss from baseline in BCVA score as assessed by the ETDRS chart at a starting distance of 4 m
- Change from baseline in low luminance visual acuity (LLVA) as assessed by the ETDRS chart at a starting distance of 4 m
 - Note: In the protocol, LLVA was referred to as BCVA score as assessed by ETDRS chart under low luminance conditions.
- Patients with < 15 letters loss from baseline in LLVA score as assessed by the ETDRS chart at a starting distance of 4 m
- Change from baseline in binocular maximum reading speed as assessed by Minnesota low-vision reading test (MNRead) or Radner Charts
- Change from baseline in monocular maximum reading speed as assessed by MNRead or Radner Charts
- Change from baseline in National Eye Institute Visual Functioning Questionnaire 25-item Version (NEI VFQ-25) composite score
- Change from baseline in NEI VFQ-25 near activity subscale score
- Change from baseline in NEI VFQ-25 distance activity subscale score
- Change from baseline in Mean Functional Reading Independence (FRI) Index score

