For endpoints that are defined in terms of change from baseline, patients who do not have a baseline value reported for a particular assessment will be excluded from the change-from-baseline analyses for that assessment. Similarly, in general, patients who do not have at least one post-baseline value reported for a particular assessment will be excluded from the change from baseline analyses for that assessment. For selected endpoints, sensitivity analyses that include patients without observed post-baseline values will be performed.

For continuous outcomes, a data-as-observed approach with a mixed-effect model repeated measures (MMRM) will be used to handle missing data, which assumes that the missing data are missing at random (MAR). For binary outcomes, analysis of the outcome at a specific time point will be based on observed data, unless otherwise noted. Study discontinuations and the reasons for study discontinuations will be summarized by treatment arm (see Section 4.3) to evaluate the potential impact of missing data on the results. In addition, a number of sensitivity analyses to assess the robustness of the primary analysis results to missing data assumptions will be performed.

For patient-reported outcome measures (e.g., NEI VFQ-25), there are two types of missing data: missing at the form level and missing at the item level. Missing form level data will be handled as described above. Missing item values will follow the rules for scoring and handling of missing item-level data as described in the user's manual.

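### The Week 96 analyses of <15-letter loss in BCVA and LLVA drop patients not seen at Week 96 and ignore their earlier scores, so rates of maintained vision are overstated if vision loss drives dropout

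*SAP*

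**What the plan says.** SAP 2.1.2 lists two binary vision secondaries, "Patients with < 15 letters loss from baseline in BCVA score" and "Patients with < 15 letters loss from baseline in LLVA score", with formal testing at Week 96.

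The analysis rule appears twice. SAP 4.5 says: "For binary outcomes, analysis of the outcome at a specific time point will be based on observed data, unless otherwise noted". SAP 4.5.2 says: "In general, binary secondary endpoints will be analyzed using a logistic regression model", adjusted for arm, the baseline value and the baseline covariates, and then "Analyses will be based on the observed data for the timepoint, with no imputation for missing data". No exception is noted for these two endpoints.

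The same letter scores are handled differently as continuous outcomes. BCVA and LLVA change are analysed by MMRM under MAR, with BCVA entering at "Weeks 12, 24, 36, 48, 60, 72, 84, and 96 that are in common between the Q4W and Q6W dosing arms". For the exploratory endpoint of <20% growth in GA area, SAP 4.5.3 does look back to earlier visits when the timepoint is missing. The imputation and tipping-point methods in SAP 4.5.1.4 cover GA area only. SAP 4.5 also mentions sensitivity analyses for selected endpoints that would bring in patients lacking any post-baseline value, but it names neither these endpoints nor a method for them.

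**The concern.** One measurement is analysed under two missing-data approaches, and the binary one sets aside data already collected. A patient recorded as 20 letters down at Week 84 who then leaves counts in the MMRM but disappears from the responder analysis. If patients who lose vision leave more often, those still present at Week 96 are a favourable selection and the reported proportions maintaining vision are too high. Such proportions are easy to quote on their own, so absolute accuracy matters as well as the contrast between arms. Two further things are at stake: the contrast itself, if the link between vision and dropout differs between drug and sham, and the precision that the earlier visits could supply.

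**Working it through.** **The plan's own two-year figure.** The documents give no sample size or power for these endpoints. The only two-year dropout figure is in Protocol 6.1, for microperimetry: "with the assumption of a 25% dropout rate by 2 years". That calculation reproduces. With 46 × 0.75 = 34.5 per group, difference 6.91, SD 9.88 and two-sided α = 0.05, a two-sample t-test has 81.7% power against the stated 80%.

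**What is discarded.**
- BCVA has eight common analysis visits (SAP 4.5.2), seven of them before Week 96. LLVA is measured after baseline at Weeks 24, 48, 72 and 96 (Protocol Appendix 1), so three come before Week 96.
- At 25% dropout, 0.25 × 936 = 234 patients leave the Week 96 binary analysis, and 312 × 0.75 = 234 remain per comparison arm. The standard error rises by at most 1/√0.75 = 1.155.
- At 15% (the planning figure for 48 weeks), about 140 patients leave and the factor is at most 1/√0.85 = 1.085.

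**Rate bias, simulation A.** Assumptions: mean BCVA change −10 letters at Week 96, slope SD 11, visit noise SD 5, eight visits, 25% dropout. The SD of the Week 96 change is √(11² + 5²) = 12.08, so the true rate of <15-letter loss is Φ(5/12.08) = 66.0%.

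| Dropout odds per 10 letters lost | Observed-only rate | Overstatement |
|---|---|---|
| × 1.3 | 67.6% | 1.6 points |
| × 1.65 | 68.8% | 2.8 points |
| × 2.1 | 70.5% | 4.5 points |

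**Rate bias, simulation B.** Assumptions: 312 per arm, 400 runs, slope SD 14, residual SD 6, dropout odds doubling per 10 letters lost. The sham loss rates are anchored on the natural-history figures in Protocol 3.3.2.1 (41% and 15% with three-line loss at two years; midpoint 28%). The treatment effects are assumed. The table gives rates of ≥15-letter loss, sham/active, with seven earlier visits.

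| Dropout | Complete data | Observed-only | Multiple imputation |
|---|---|---|---|
| 25% | 27.9/18.1% | 23.7/14.8% | 27.9/18.2% |
| 15% | 28.1/18.1% | 25.6/15.9% | 28.1/18.0% |
| 25% | 40.9/28.9% | 35.9/24.7% | 40.9/29.1% |
| 25% | 14.9/9.1% | 11.8/7.0% | 14.9/9.2% |

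Loss is understated, and so maintained vision overstated, by 2.1 points (9.1 − 7.0) to 5.0 points (40.9 − 35.9). At 15% dropout the bias is 2.2 to 2.5 points. Imputation from earlier visits removes it when dropout depends on observed vision.

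**Treatment contrast.**
- Same mechanism in both arms: in B (28% vs 18%, 25% dropout) the odds ratio is 1.80 observed-only against 1.76 with complete data, and the risk difference is 8.9 against 9.8 points. In A, with an assumed benefit (mean change −7 vs −10), it is about 1.51 true against 1.51 to 1.54 observed-only.
- Vision-driven dropout in sham only: in B with no true effect, the observed-only risk difference is −4.4 points (odds ratio 0.79), against 0.0 (1.00) with imputation. With a true 28% vs 18%, the observed-only difference is 5.6 points against 9.9. In A the distortion is 1.4 to 4.4 points. Each of these runs against the drug.

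**Precision.**
- In B, with 25% dropout unrelated to vision and seven earlier visits, the SD of the log odds ratio is 0.227 observed-only against 0.205 imputed (0.227/0.205 = 1.11). For the risk difference it is 0.0379 against 0.0348 (1.09).
- In A (600 replicates of n = 312), the variance of a single rate falls by 14% to 23% with imputation (0.0295 to 0.0273, and 0.0317 to 0.0279).
- In B, imputation recovers almost everything, because visits are assumed to be highly correlated; this is towards the favourable end. A three-visit run gave 0.222 against 0.201, but it reused the BCVA variances and is not evidence about LLVA.

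**The case against.** The best case for leaving the plan alone is that little rests on these endpoints. They are not among the three key secondaries in SAP 4.5.2.1. Continuous LLVA is one of the three, and continuous BCVA and LLVA already receive an all-visit MAR analysis. Patients and evaluators are masked. Stopping treatment is distinct from leaving the study, Week 48 and Week 96 attendance is stressed (Protocol 4.6.2), and off-treatment data are kept (SAP 4.5). Discontinuations and their reasons will be tabulated by arm. All of this stands, and it limits the importance of the point. It does not correct the reported rates.

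Three stronger readings are tempting and are not supported.

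- *That the logistic analysis is valid only if dropout depends on baseline covariates alone.* The planned effect measure is an odds ratio. It is unaffected by dropout that depends on arm and modelled covariates, and nearly unaffected when vision drives dropout equally in both arms.
- *That the treatment comparison is therefore biased.* That needs a mechanism that differs by arm. The documents neither show one nor exclude one, given that a sham procedure is compared with a real injection.
- *That a quarter of patients contribute nothing.* The 25% was set for microperimetry, and these patients still contribute to the MMRMs and, if seen then, to the Week 48 evaluation. Likewise, seven discarded visits applies to BCVA only.

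**Conclusion.** The point holds as a modest improvement to non-key secondaries. The plan omits patients unseen at Week 96 from both <15-letter analyses and ignores their earlier scores, with no named sensitivity analysis. If vision loss drives dropout, maintained-vision rates are overstated by about 1.5 to 4.5 points at 25% dropout (5.0 in the highest-loss scenario run) and by roughly half that at 15%. These sizes rest on assumed progression, variance and strength of the dropout link, and on a dropout figure borrowed from another endpoint. If dropout is unrelated to vision, the rates are unbiased and only precision is lost, by an amount that depends on visit-to-visit correlation and has not been shown for LLVA. The odds ratio is essentially sound unless the mechanism differs by arm.

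**What to change.** In SAP 4.5.2, for <15-letter loss in both BCVA and LLVA:

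1. Multiply impute the continuous letter score by visit within treatment arm (sham pooled), using sequential regression on all earlier visits and the SAP covariates, under MAR.
2. Dichotomise each completed data set at Week 96, fit the planned logistic model and combine by Rubin's rules.
3. Report the observed-case logistic model alongside as a sensitivity analysis.
4. Add a missing-not-at-random check (delta-adjusted or reference-based).

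Do not carry over the GA imputation rules in SAP 4.5.1.4 (non-negative increments, linear interpolation of gaps) or the look-back rule in SAP 4.5.3. They suit irreversible growth, whereas acuity can recover.

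The cost is SAP wording and a modest amount of new programming, since the GA code does not transfer directly. The main result still relies on MAR, which the SAP already accepts for continuous acuity; step 4 tests how far the conclusion depends on it.

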4.5.2.1 Type I Error Management

Significance testing for secondary efficacy endpoints will be gated on the success of the primary efficacy endpoint evaluated at Week 48. Secondary efficacy endpoints will be tested at Week 96 for the lampalizumab dose frequency or frequencies (Q4W or Q6W) and patient populations (overall or biomarker-positive) found to demonstrate statistically significant treatment effect for the primary efficacy endpoint.

The following secondary efficacy endpoints will be tested in the order listed below:

- Change from baseline in number of absolute scotomatous points at Week 96 as assessed by mesopic microperimetry
 - Note: Due to small sample size, statistical inferences for this endpoint to be based on pooled data from Studies GX29176 and GX29185.
- Change from baseline in LLVA at Week 96 as assessed by ETDRS chart at a starting distance of 4 m
- Change from baseline in binocular maximum reading speed at Week 96 as assessed by MNRead or Radner Charts

A list of the hypothesis testing of the key secondary clinical endpoints is given below:

- H_{05} : There is no difference between lampalizumab and sham with regard to mean change from baseline in the number of absolute scotomatous points at Week 96.
- H_{06} : There is no difference between lampalizumab and sham with regard to mean change from baseline in LLVA at Week 96.
- H_{07} : There is no difference between lampalizumab and sham with regard to mean change from baseline in binocular maximum reading speed at Week 96.

For each lampalizumab dosing frequency and patient population found to be statistically different from sham for the test of the primary endpoint, testing of the three key secondary endpoints will be performed (e.g. if H_{01} is positive per the Type I error control plan, then the key secondary endpoints would be tested for the Q4W dose frequency in the overall patient population). The aim is to manage the Type I error rate with respect to conclusions about secondary endpoints within a given dose frequency and patient population. Thus, within each dose frequency and patient population, Type I error for key secondary endpoints will be controlled using a fixed sequencing approach by testing the secondary endpoint hypotheses sequentially in the order specified above, beginning with H_{05} .

All hypotheses for the key secondary endpoints will be tested for significance at the study level, except for H₀₅. The secondary endpoint of number of absolute scotomatous points will be based on the microperimetry-analysis population, which is estimated to be 10-15% of the total ITT population. Microperimetry was assessed in a subset of patients at selected study sites only. For this secondary endpoint, data from both Studies GX29176 and GX29185 will be combined to achieve a sample size sufficient to evaluate and test for treatment differences with a reliable level of precision.

As a consequence of this, for analyses of secondary efficacy endpoints at the individual study level:

- For H₀₅, the study-level p-value will be presented. However, interpretation of significance in a confirmatory manner will be based on the analysis of pooled data from Studies GX29176 and GX29185.
- H₀₆ will be tested in a confirmatory manner at the study-level if and only if, based on an analysis of pooled data from Studies GX29176 and GX29185, H₀₅ is rejected (i.e., pooled analysis $p \leq 0.0496$).
- H₀₇ will be tested in a confirmatory manner at the study-level if and only if H₀₆ is rejected at the study-level

As noted above, significance testing for H₀₅ will not be done at the study level, but rather interpretation of significance in a confirmatory manner will be based on the analysis of pooled data from Studies GX29176 and GX29185 for the microperimetry-based endpoint.

All hypothesis tests for the secondary endpoints will be on the basis of a two-sided alpha level of 0.0496.

4.5.2.2 Subgroup Analyses

Exploratory subgroup analyses will be performed to evaluate the consistency of the analysis results for two of the key secondary efficacy endpoints (change from baseline in LLVA at Week 96 and change from baseline in binocular maximum reading speed at Week 96). Subgroup analyses will not be performed at the study level for the key secondary endpoint of change from baseline in number of absolute scotomatous points at Week 96 due to the smaller sample size in the microperimetry-analysis population.

The subgroups evaluated for secondary endpoints will be based on demographic and baseline characteristics, as done for the primary efficacy endpoint (see Section 4.5.1.3). For binocular maximum reading speed, an additional subgroup analysis based on eye with greater BCVA at baseline (study vs. fellow) will be performed. Patients with equivalent baseline BCVA in the study and fellow eye (if any) will be grouped with patients with greater BCVA in the study eye for this subgroup analysis.

For analysis maximum reading speed assessed by MNRead or Radner charts, additional subgroup analyses by reading chart type (MNRead or Radner) will also be performed to assess the consistency of findings across the two reading charts.

For each endpoint, a MMRM similar to that specified for the main analysis (Section 4.5.2) will be used for each subgroup analysis based on the data subset for the patient subgroup of interest. Baseline covariates included in the main analysis but no longer relevant given the subgroup of interest will be excluded from the model. The estimated treatment effects (lampalizumab vs. sham) and corresponding 95% CIs from the models will be displayed graphically for each lampalizumab treatment arm and each level of the subgroups specified (e.g. via forest plots).

